### **5. ADVERSE EFFECTS**

#### **5.1 DEFINITIONS**

Adverse Event (AE): any untoward medical occurrence in a patient or clinical study subject.

Serious Adverse Event (SAE): any untoward and unexpected medical occurrence or effect that:

- Results in death
- Is life-threatening – *refers to an event in which the subject was at risk of death at the time of the event; it does not refer to an event which hypothetically might have caused death if it were more severe*
- Requires hospitalisation, or prolongation of existing inpatients' hospitalisation
- Results in persistent or significant disability or incapacity
- Is a congenital anomaly or birth defect

Medical judgement should be exercised in deciding whether an AE is serious in other situations.

Important AEs that are not immediately life-threatening or do not result in death or hospitalisation but may jeopardise the subject or may require intervention to prevent one of the other outcomes listed in the definition above, should also be considered serious.

#### **5.2 REPORTING PROCEDURES**

All adverse events will be reported. Depending on the nature of the event the reporting procedures below should be followed. Any questions concerning adverse event reporting should be directed to the Principal Investigator in the first instance.

### 5.2.1 NON SERIOUS AEs

All such events, whether expected or not, will be recorded.

### 5.2.2 SERIOUS AEs

An SAE form should be completed and faxed to the Chief Investigator within 24 hours. However, and hospitalisations for elective treatment of a pre-existing condition do not need reporting as SAEs. All SAEs should be reported to Ethics Committee where in the opinion of the Principal Investigator, the event was:

- 'related', ie resulted from the administration of any of the research procedures; and
- 'unexpected', ie an event that is not listed in the protocol as an expected occurrence

Reports of related and unexpected SAEs should be submitted within 15 days of the Chief Investigator becoming aware of the event, using the NRES SAE form for non-IMP studies. The Chief Investigator must also notify the Sponsor of all SAEs.

Local investigators should report any SAEs as required by their Local Research Ethics Committee, Sponsor and/or Research & Development Office.

## 6. ASSESSMENT AND FOLLOW-UP

Participants will receive a week post-exposure test battery to assess recovery. After this, there will be no follow up in the Audiology Department. If abnormal results are highlighted at any stage, participants will be excluded from the study and as consented, a letter containing the results will be sent to the GP. Participants will subsequently be excluded from the study and information destroyed.

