## **2. STUDY OBJECTIVES**

- i) To identify if there is a relationship between previous sound exposure levels and TTS and tinnitus after a single loud noise event.

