### **3.2 METHODS**

Screening - Participants will be asked about the health of their ears and ears will be examined to ensure there are no abnormalities (Otoscopy). A hearing test (PTA) will then be performed; This test will involve participants listening to a series of tones at different pitches and volumes through headphones and participants will press a button whenever they hear a tone. The researcher will also undertake a structured interview to assess noise exposure history (NESI) and the results from the screen will see if you are eligible to participate in this research. With participants consent, if any abnormalities are detected at any point, your GP will be informed with a copy of the results. Participants will subsequently be excluded from the study and information destroyed. Example of NESI question: I'd like you to estimate how noisy it was when you [engaged in the activity] by answering this question: If you and I were 4 feet apart in that situation, which of the following would you need to do to communicate with me? [The interviewer presents the six options from the Speech Communication Table.]

Each session will require 35 minutes (35 x 3 = 105 minutes overall).

SESSION ONE - Prior to noise exposure (continued same day after screening passed if eligible):

Test battery - High frequency audiometry, Distortion Product Otoacoustic Emissions, Middle Ear Muscle Reflex, Speech in Noise test, Tinnitus Functional Index (Around 35 minute testing time with breaks if required)

- Extended Frequency Pure Tone Audiometry (~ 8 minutes)

Similar to Screening, participants will be asked to press the button when they hear a sound through the headphones in a sound proof booth.

- Distortion Product Otoacoustic Emissions (~ 5 minutes)

A small tip will be placed in participants' ear and they will hear a sound. The tip measures a response from hair cells in the cochlea and they will not need to do anything.

- Middle Ear Muscle Reflex (~ 8 minutes)

A small tip will be placed in both ears and again a sound heard however this sound will gradually get louder until an involuntary muscle reflex is noted.

- Speech in Noise Test (~ 5 minutes)  
Participants will be asked to repeat back a list of words as best as they can.
- Tinnitus Functional Index (~ 8 minutes)  
Participants will be given a self-report sheet in which they have to fill out aspects of any tinnitus experienced.

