SESSION TWO - Exposure at single loud music event (Important that this is part of participants' normal recreational routine, and specifically require that attendance is not prompted by participation in this study): Participants to use sound level meter provided from the Audiology Department at Charing Cross Hospital to measure sound levels inside the loud event.

Morning after exposure: Repeat test battery from session one - Ideally as soon as event is over.

SESSION THREE: 1 week later (recovery): Repeat test battery.

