#### **4.4 EXCLUSION CRITERIA**

- No permanent tinnitus or hyperacusis (sensitivity to loud sounds) which would mean participants are unable to undertake all testing and a high exposure event
- Any contraindications for testing i.e. excessive wax, infections
- One or more frequencies 0.25 Hz to 8 kHz > 20 dB HL in either ear
- Not involved in current research or have recently been involved in any research prior to recruitment

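### The rule to exclude participants and destroy their data for abnormal results is not confined to screening, so it can remove the outcome under study, and it conflicts with the five-year retention rule

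*Combined protocol and SAP*

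**What the plan says.** Section 6 (Assessment and Follow-up) opens with the test battery one week after exposure. It then says: "If abnormal results are highlighted at any stage, participants will be excluded from the study". After mentioning the letter to the GP it adds: "Participants will subsequently be excluded from the study and information destroyed".

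Section 3.2 (Methods) has a parallel rule in its screening paragraph: "if any abnormalities are detected at any point, your GP will be informed with a copy of the results". The same exclusion and destruction sentence follows.

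The objective in section 2 is the "relationship between previous sound exposure levels and TTS and tinnitus after a single loud noise event". Section 3.2 repeats the session-one battery (extended-frequency audiometry, DPOAE, MEMR, speech in noise, TFI) the morning after the event and again for recovery: "SESSION THREE: 1 week later (recovery): Repeat test battery".

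The only numerical hearing limit is an entry criterion. Section 4.4 excludes "One or more frequencies 0.25 Hz to 8 kHz > 20 dB HL in either ear", and section 4.3 states the matching inclusion limit.

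On retention, section 7 requires data to be stored for at least five years after the study ends, and section 8.3 says all data are kept for five years. Neither makes an exception for excluded participants. On non-serious adverse events, section 5.2.1 says: "All such events, whether expected or not, will be recorded".

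**The concern.** A marked threshold shift or new tinnitus after the event is what the study sets out to measure, yet it can naturally be called an abnormal result. If the rule is applied at sessions two or three, whether a participant stays in the data depends on the outcome. Someone removed after session two also has no recovery measurement, although session three exists to provide it.

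If the groups start with similar hearing and conditioning protects, more of the less-exposed group is lost and the difference shrinks. The groups are formed by exposure history rather than randomised (section 3), so the more-exposed group may start with worse thresholds. A fixed threshold limit then takes more of that group, and the difference can stay the same, grow, or appear where there is none.

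With no definition of abnormal after entry, the direction cannot be predicted. With the data destroyed, no sensitivity analysis can recover what was lost. Section 7 names no analysis set and no missing-data rule that would limit the damage.

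**Working it through.** **Comparing the sections**

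1. *Stage.* Section 6 applies the rule at any stage, in the paragraph on post-exposure follow-up. Section 3.2 applies it at any point. Nothing restricts it to screening or exempts event-related change.
2. *Definition.* The 20 dB HL limit covers 0.25–8 kHz audiometry at entry. No limit is given for any test in the repeated battery.
3. *Schedule.* Session three measures recovery, which requires participants with a shift at session two to remain.
4. *Retention.* Destroying information cannot be squared with keeping all data for five years unless an exception is written, and none is.
5. *Adverse events.* If a result counts as an adverse event, destruction also conflicts with section 5.2.1. No section says whether an expected temporary shift counts.

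**Illustration of the bias**

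The plan gives no effect size, SD, alpha or power, so there is no figure to reproduce. Only the 20 per group (section 3) and the 20 dB HL entry limit come from the protocol. Everything else is assumed: temporary shift T = max(0, X), with X normal, mean m = 10 dB (less exposed) or 5 dB (more exposed), SD s = 5; baseline normal, SD 5, truncated at 20 dB HL.

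*Full data:* E[T] = mΦ(m/s) + sφ(m/s).
- Less exposed: 10(0.9772) + 5(0.0540) = 10.04.
- More exposed: 5(0.8413) + 5(0.2420) = 5.42.
- Difference: about 4.63 dB before rounding.

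*Abnormal means a shift of at least c:* the mean among those kept is {m[Φ(b) − Φ(a)] − s[φ(b) − φ(a)]}/Φ(b), with a = −m/s and b = (c − m)/s. For c = 15:
- Less exposed: [10(0.8413 − 0.0228) − 5(0.2420 − 0.0540)]/0.8413 = 8.61.
- More exposed: [5(0.9772 − 0.1587) − 5(0.0540 − 0.2420)]/0.9772 = 5.15.
- Difference: 3.46 dB, and 3.46/4.63 = 0.75, a 25% reduction.

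*Abnormal means baseline plus shift above 20 dB HL* (borrowed from the entry limit): the same formula with c = 20 − baseline, averaged over the baseline distribution.

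| Definition (baselines in dB HL, less v more exposed) | Excluded, less v more exposed | Difference kept | Change |
|---|---|---|---|
| Shift ≥ 10 dB | 50% v 16% | 2.0 dB | −56% |
| Shift ≥ 15 dB | 16% v 2% | 3.5 dB | −25% |
| Shift ≥ 20 dB | 2% v 0% | 4.4 dB | −5% |
| Above 20 dB HL, 8 v 8 | 38% v 15% | 3.4 dB | −27% |
| Above 20 dB HL, 0 v 0 | 8% v 2% | 4.2 dB | −9% |
| Above 20 dB HL, 6 v 12 | 28% v 30% | 4.7 dB | +1% |
| Above 20 dB HL, 5 v 12 | 24% v 30% | 4.9 dB | +6% |
| Above 20 dB HL, 5 v 14 | 24% v 38% | 5.3 dB | +15% |

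In the 8 v 8 case, 20 × 0.62 ≈ 12 and 20 × 0.85 = 17 participants remain.

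*No true difference* (mean 7 dB in both groups, SD 5, 20 dB HL limit, baselines 5 v 12): 13% v 41% are excluded and the kept means are 6.36 v 4.83 dB, a false difference of about 1.5 dB in the direction of protection.

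*Power, under a second set of assumptions* (mean shift 8 v 4 dB, SD 5, no floor at zero, two-sided 5%): with everyone kept, SE = √(25/20 + 25/20) = 1.58 and power = Φ(4/1.58 − 1.96) = 72%. Excluding shifts above 20, 15 or 10 dB leaves differences of 3.9, 3.4 or 2.3 dB and approximate power of 71%, 63% or 39%.

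**The case against.** The strongest reply is that the harmful reading is not what was meant. The exclusion and destruction sentence also stands in the screening paragraph of section 3.2, after otoscopy and audiometry, and discarding people for a temporary shift would defeat a study of temporary shift. Incidental pathology or screening failure is a coherent intent. That is plausible, but section 6 is the follow-up section and says the opposite of a restriction. If the narrow meaning was intended, saying so is a short edit. If it was not, the rule selects on the outcome.

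Second, the 20 dB HL scenarios borrow a limit from a test that is not in the post-event battery, and they use one threshold per person where the criterion covers any frequency in either ear. This stands as a limit on the figures. All the enlarged and false differences above rest on that scenario, whereas cut-offs on the shift itself only shrink the difference. The argument about selection does not depend on either scenario.

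Third, section 8.3 already combines destruction of interview recordings with five-year retention, so destroying excluded data could be read as another exception. The recordings survive as transcripts, though, and excluded participants' information would not survive in any form.

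Fourth, the adverse-event conflict is conditional. That is correct, and it is put here as a query only.

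**Conclusion.** The concern holds. As written, the rule permits exclusion on the outcome with permanent loss of the data, works against the recovery session, and contradicts the retention statements. With 20 per group, a few such removals matter, and unlike most gaps in a plan this one cannot be repaired at analysis.

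The documents determine neither the size nor the direction of the bias. The illustrative changes run from −56% to +15%, and are small when the limit is rarely reached. None is a bound, and all rest on assumed shifts, SDs and baselines. What is certain is the wording. Whether the sponsor meant it to reach sessions two and three is not known.

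**What to change.** Reword sections 3.2 and 6, and add a line to section 7:

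1. Limit exclusion and data destruction for abnormal results to eligibility at screening, before exposure, where abnormal means failing the criteria in sections 4.3 and 4.4. Session-one results obtained after screening is passed are kept as baseline data.
2. State that any change from session one in extended-frequency audiometry, DPOAE, MEMR, speech in noise or TFI at sessions two and three is outcome data, kept and analysed in the participant's original exposure group.
3. If the word abnormal is still used after exposure, define it for each test and state that it removes neither the participant nor the data.
4. Flag results explained by incidental ear problems of the kind in section 4.4 ("Any contraindications for testing i.e. excessive wax, infections"). Handle them by a rule set in section 7 before analysis, such as a sensitivity analysis without them.
5. Reconcile destruction with the five-year retention in sections 7 and 8.3, saying whether screening failures are an exception, and with section 5.2.1 where a result counts as an adverse event.

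The GP letter is unaffected. The cost is protocol wording, an amendment and matching participant information, with no added participants or procedures. The sponsor should check how the amendment is classified and whether existing consent covers keeping these data. Otoscopy is listed only at screening, so flagging under item 4 would rest on what the tester notes or the participant reports, unless the sponsor chooses to add a check.

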## 7. STATISTICS AND DATA ANALYSIS

The quantitative data will be analysed by the researcher at Charing Cross Hospital, Imperial Healthcare NHS Trust. Data and all appropriate documentation will be stored for a minimum of 5 years after the completion of the study, in line with trust protocol.

## 8. REGULATORY ISSUES

### 8.1 ETHICS APPROVAL

The Study Coordination Centre has obtained approval from the Research Ethics Committee (REC) and Health Research Authority (HRA). The study must also receive confirmation of capacity and capability from each participating NHS Trust before accepting participants into the study or any research activity is carried out. The study will be conducted in accordance with the recommendations for physicians involved in research on human subjects adopted by the 18th World Medical Assembly, Helsinki 1964 and later revisions.

### 8.3 CONFIDENTIALITY

The Principal Investigator will preserve the confidentiality of participants taking part in the study. All information which is collected during the research will be kept strictly confidential. Participants will be given a unique ID number as a substitute for personal information and this will be attached to any results from tests. This will be kept in compliance with the Data Protection Act. This anonymised data will be stored and may be published. Any other personal information will be stored on a password-protected database and only accessible to the Principle Investigator. This will be kept separately from documentation of results, ensuring information is not matched and avoid accidental identification. The NESI Structured Interview will be recorded on a digital device and transcribed; any recorded data will then be destroyed from the digital device. All of the data will be kept for 5 years as per study policies.

### 8.4 INDEMNITY

Imperial College Healthcare NHS Trust holds standard NHS Hospital Indemnity and insurance cover with NHS Litigation Authority for NHS Trusts in England, which apply to this study.

### 8.5 SPONSOR

Imperial College Healthcare NHS Trust will act as the main Sponsor for this study.

### 8.6 AUDITS

The study may be subject to inspection and audit by Imperial College Healthcare NHS Trust under their remit as Sponsor, the Study Coordination Centre and other regulatory bodies to ensure adherence to GCP.

## 9. STUDY MANAGEMENT

The day-to-day management of the study will be co-ordinated through the Principal Investigator.

## 10. PUBLICATION POLICY

The results will be included in the final MSc Project and in ethical applications for the secondary phase, where the evaluation will take place. The results will be published in peer reviewed journals, conference papers and research presentations. The anonymity of the participants will be ensured when publishing. If participants wish to receive a summary report of the findings at the end of the study then they may request this.

All publications and presentations relating to the study will be authorised through the Chief Investigator and Academic supervisor. If there are named authors, these will include at least the trial's Chief Investigator, Statistician and Trial Coordinator. Members of the TMG and the Data Monitoring Committee will be listed and contributors will be cited by name if published in a journal where this does not conflict with the journal's policy. Authorship of parallel studies initiated outside of the Trial Management Group will be according to the individuals involved in the project but must acknowledge the contribution of the Trial Management Group and the Study Coordination Centre.

